1.1.1. Primary Estimand(s)

The primary estimand is defined according to the primary objective and is in alignment with the primary endpoint. It includes the following 4 attributes:

- Population: Patients with achondroplasia, as defined by inclusion/exclusion criteria;
- Variable: Height Growth at 24 months;
- Height Growth = (Observed Change from Baseline (from study C4181005) in standing height (cm))/(Expected Change from Baseline (cm)[Merker et al, 2018]¹)

- Intercurrent event(s): Withdrawal and all events leading to missing data will be excluded from efficacy analysis and will not have their data imputed;
- Population-level summary: Mean Height growth at 24 months adjusted for age and gender.

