2. ENDPOINTS AND BASELINE VARIABLES: DEFINITIONS AND CONVENTIONS

2.1. Primary Endpoint(s)

Safety

Safety and tolerability of recifercept as assessed through frequency and severity of AEs/SAEs.

Efficacy

Increase in height growth above expected in reference population [Merker et al, 2018].

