4.2.1. Analyses for Longitudinal Continuous Endpoints

Mixed-effect, repeated measures (MMRM) models will be used. The fixed effects of treatment, visit, treatment-by-visit interaction, age and gender will be included. Visit will be modeled as a categorical covariate. (If the model does not converge then Visit will be modeled as a continuous covariate.) Unstructured covariance matrix will be assumed for the model errors. Compound symmetry covariance matrix will be used if the model with unstructured variance covariance doesn't converge.

When modeling the change from baseline values, the variable for visit will start with the first post-baseline visit. At each visit, estimates of least square mean (LSM) values and the LSM differences between treatment groups will be derived from the model. The corresponding p-values and 95% confidence intervals will also be derived from the model.

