5. ANALYSES AND SUMMARIES

5.1. Primary Endpoint(s)

5.1.1. Increase in height growth above expected in reference population

5.1.1.1. Main Analysis

- Estimand strategy: Hypothetical ([Section 1.1.1](#)).
- Analysis set: FAS ([Section 3](#)).
- Analysis methodology: Change from baseline relative to Merker (2018) will be analyzed using MMRM including data from Months 3-24 with gender (and possibly age), and whether a subject has switched doses of recifercept as covariates, subject (and/or time) as a random effect and an unstructured covariance matrix ([Section 4.2.1](#)).
- Intercurrent events and missing data: Data after study drug discontinuation and rescue will be excluded; intermediate missing values will not be imputed.
- The sample size, mean, standard deviation, median, minimum, and maximum at the baseline and postbaseline visits for observed standing height and change from baseline will be presented for each treatment arm.
- The least-squares (LS) means, the 95% confidence interval for the LS means, the difference between the LS means for each pair of treatment groups, and the corresponding 95% confidence interval will be presented for change from baseline in standing height for all postbaseline visits.

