Appendix 2.2. Endpoint Derivations

Height Growth

The primary efficacy endpoint is H defined by the following:

$$H_{ijkl} = \frac{Y_{ijkl} - Y_{i0kl}}{Z_{jl} - Z_{0l}},$$

where Y_{ijkl} is the observed standing height for the i th subject, at month j on dose k with gender factor l ($j=0$ denotes baseline measurement) and Z_{jl} is the mean expected standing height based on Merker for subject i 's age.

Mean expected standing height from Merker is sorted by 6 months up to age 4, while means expected values for children > 4 years are sorted per annum. Linear interpolation will be employed to calculate mean expected values so that mean standing height are sorted at 6 month intervals for children > 4 years. SAS code for the linear interpolation calculation will be provided in Appendix 4.

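### For the height-growth ratio H, the LS-mean p-value defaults to a test of H = 0 (no growth), while no drug effect is H = 1

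*SAP*

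**What the plan says.** SAP 2.1 gives the primary efficacy endpoint as "Increase in height growth above expected in reference population". SAP 1.1.1 defines the variable as observed change in standing height divided by the change expected from the published achondroplasia reference. Appendix 2.2 gives the same ratio as a formula, introduced by "The primary efficacy endpoint is H defined by the following".

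SAP 5.1.1.1 states the model: "Change from baseline relative to Merker (2018) will be analyzed using MMRM including data from Months 3-24", with a reference to Section 4.2.1. Its own output list begins "The least-squares (LS) means, the 95% confidence interval for the LS means, the difference between the LS means for each pair of treatment groups" and goes on to the interval for the differences. It mentions no p-values.

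The p-values come from SAP 4.2.1: "At each visit, estimates of least square mean (LSM) values and the LSM differences between treatment groups will be derived from the model", followed at once by "The corresponding p-values and 95% confidence intervals will also be derived from the model". The Appendix 4 code requests LS means by dose. It names no test value, and it neither subtracts 1 from the response nor takes logs.

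Two further statements matter. SAP 4.1 says that the protocol has no statistical hypotheses. Protocol 9.3.2 and the synopsis define the co-primary efficacy endpoint as reference growth plus 50%, which on this scale is H = 1.5.

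**The concern.** The study is open label and has no control arm, so the external reference is the only comparator that can show whether children grew more than expected. On the ratio scale, growth equal to the reference is H = 1, and H = 0 means that treated children did not grow at all. Unless told otherwise, the software compares an LS mean with 0. For H that null hypothesis is not in question for children selected because they are still growing.

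A reader who sees a small p-value beside each dose in the primary efficacy results may take it as evidence of efficacy. It would be small even if the drug did nothing.

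**Working it through.** **Inputs from the documents.** About 63 participants and 3 doses (SAP 1.2). Anthropometry every 3 months (protocol 8.1.1), so Months 3 to 24 give 8 visits and 3 × 8 = 24 dose-by-visit LS means. The plan gives no alpha, power or sample-size figure for H, so there is no stated figure to reproduce.

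**Assumptions.** Equal split, 63/3 = 21 per dose, with 15 and 10 as smaller cases. Two-sided 5%, taken from the 95% intervals. The SD of H is not in the documents, so a range is shown. A one-sample t test stands in for the LS-mean test (complete data, no covariates).

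**Formula.** With true mean 1 and null value h0, the noncentrality is (1 − h0)/(SD/√n), on n − 1 degrees of freedom. For h0 = 0, n = 21 and SD = 1.0, the standard error is 1/√21 = 0.218, the noncentrality is 4.58 and the critical t is 2.086, so the rejection probability is 0.992. For h0 = 1 the noncentrality is 0 and the rejection probability is 0.05 for any SD and n.

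Probability of p < 0.05 against H = 0 when true H = 1:

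| SD of H | n = 21 | n = 15 | n = 10 |
|---|---|---|---|
| 0.5 | >0.999 | >0.999 | >0.999 |
| 0.75 | >0.999 | 0.998 | 0.962 |
| 1.0 | 0.992 | 0.949 | 0.803 |
| 1.25 | 0.936 | 0.821 | 0.616 |
| 1.5 | 0.828 | 0.671 | 0.469 |
| 2.0 | 0.587 | 0.438 | 0.293 |

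The probability stays at or above 0.90 up to an SD of 1.34 (n = 21), 1.11 (n = 15) or 0.87 (n = 10).

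**Across visits.** A simulation of all 24 tests with true H = 1 assumed expected growth of 3.5 to 5 cm/year, a between-child CV of 20 to 40% and a measurement SD of 0.3 to 0.7 cm. Against 0, 99.4 to 100% of tests had p < 0.05 with 21 per dose, and 95.4 to 100% with 10 per dose. Against 1, the share was 4.8 to 5.2%. Month 3 is the weakest visit because expected growth, the denominator, is smallest there. In the noisiest setting the SD of H at Month 3 is about 1.2, and the test against 0 rejects 95% with 21 per dose and 65% with 10.

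**Growth at half the reference.** With true H = 0.5 and n = 21, the test against 0 rejects with probability 0.992 at SD 0.5, 0.828 at SD 0.75 and 0.587 at SD 1.0. At lower SDs the default p-value is therefore usually significant even when growth is well below the reference.

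**The case against.** The strongest reply is SAP 4.1: with no hypotheses, no decision rule depends on these p-values, and a null of 0 is written nowhere. SAP 5.1.1.1 lists only estimates and 95% intervals, and comparing such an interval with 1 is equivalent to a two-sided 5% test of H = 1. This stands, and it limits the harm. It does not remove the problem: 4.2.1 still orders p-values, every p-value has a null, and if none is named the software supplies 0.

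It can also be argued that the p-values belong only to the differences between doses. The wording allows that. However, 4.2.1 names LS means and differences together and orders p-values and intervals in one sentence, and 5.1.1.1 wants intervals for both, so the natural reading covers both.

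The code names its response height, has no dose-by-month term and prints only dose means averaged over months. The by-visit results therefore rest on the text of 4.2.1. Parts of 5.1.1.1 and Appendix 1 also speak of change in standing height. If centimetres were modelled, the default null would still be no growth, and 1 would no longer be the reference value.

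A reader might infer three stronger claims, which the material does not support:
- *Every dose would show p < 0.001 under no effect.* With n = 21 that has probability 0.95 per test at SD 0.8 but only 0.51 at SD 1.2.
- *Significance is assured even when growth is halved.* At SD 0.8 and n = 21, p < 0.05 occurs in 78% of tests and p < 0.001 in 21%.
- *The dose-difference p-values are faulty because they reject only about 5% when all doses work equally.* That is correct behaviour for a test of whether doses differ.

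**Conclusion.** The point holds for one quantity: the p-value attached to a single LS mean of H. As written, the plan leaves its null at the software default of 0, which cannot address growth above the reference. With an assumed 21 per dose and an SD of H up to 1.0, a drug with no effect would give p < 0.05 more than 99% of the time at a given dose and visit. The figure is lower with smaller groups, noisier ratios or at Month 3. All these sizes rest on the assumed SD and equal split.

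The consequence is a misleading p-value printed beside an interval that can answer the question. A reader might infer that the trial could reach a wrong formal conclusion, or could not tell an effective drug from an ineffective one. The documents do not support that, because no formal test is planned and the intervals remain usable. A null of 0 is suitable for the dose differences and for the change in arm span-height difference.

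**What to change.** In SAP 4.2.1, 5.1.1.1 and Appendix 4, state that LS means of H are compared with 1, either by modelling H − 1 or by an estimate statement with test value 1. Report the Month 24 result with its 95% interval for each dose and averaged over the three doses, since the estimand is a population-level mean. State that the default p-values against 0 are not reported for H. Keep the zero null for dose differences and for the arm span-height endpoint, and make the modelled response in the code explicitly H.

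Reconcile this with the protocol's definition of the co-primary endpoint as reference growth plus 50%. If that is the intended benchmark, say so and also compare the interval with 1.5.

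The cost is about a line of text and a line of code, with no new data. The downside for the sponsor is that the p-values will look less favourable than the default output.

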4.3. Methods to Manage Missing Data

In general, for descriptive statistics missing values will not be imputed. In addition, for safety endpoints missing values will not be imputed. Other methods for handling missing values are discussed below. Missing data methods for baseline values are discussed in [Section 2.4](#).

4.3.1. PK and CCI Data

Concentrations Below the Limit of Quantification

In all data presentations (except listings), concentrations below the limit of quantification (BLQ) will be set to zero. (In listings BLQ values will be reported as "<LLQ", where LLQ will be replaced with the value for the lower limit of quantification). For population PK modeling, BLQ will be handled by the Pfizer standard processes.

Deviations, Missing Concentrations and Anomalous Values

In summary tables of concentration data by dose, visit day and time, statistics will be calculated having set concentrations to missing if 1 of the following cases is true:

A concentration has been collected as ND (ie not done) or NS (ie no sample),

A deviation in sampling time (15% beyond the sampling time window) is of sufficient concern or a concentration has been flagged anomalous by the pharmacokineticist.

Note that summary statistics will not be presented at a particular time point if more than 50% of the data are missing.

Pharmacokinetic Parameters

Nonlinear mixed effect modeling will be performed to evaluate pharmacokinetic parameters including clearance, area under the curve at steady state over the dosing interval for recifercept. Additional details on the population PK modeling will be described in the population modeling analysis plan.

In summary tables, statistics will be calculated by setting NC values to missing; and statistics will be presented for a particular dose with ≥ 3 evaluable measurements.

If an individual subject has a known biased estimate of a PK parameter (due for example to an unexpected event such as dosing error), this will be footnoted in summary tables and will not be included in the calculation of summary statistics or statistical analyses.

5. ANALYSES AND SUMMARIES

5.1. Primary Endpoint(s)

5.1.1. Increase in height growth above expected in reference population

5.1.1.1. Main Analysis

- Estimand strategy: Hypothetical ([Section 1.1.1](#)).
- Analysis set: FAS ([Section 3](#)).
- Analysis methodology: Change from baseline relative to Merker (2018) will be analyzed using MMRM including data from Months 3-24 with gender (and possibly age), and whether a subject has switched doses of recifercept as covariates, subject (and/or time) as a random effect and an unstructured covariance matrix ([Section 4.2.1](#)).
- Intercurrent events and missing data: Data after study drug discontinuation and rescue will be excluded; intermediate missing values will not be imputed.
- The sample size, mean, standard deviation, median, minimum, and maximum at the baseline and postbaseline visits for observed standing height and change from baseline will be presented for each treatment arm.
- The least-squares (LS) means, the 95% confidence interval for the LS means, the difference between the LS means for each pair of treatment groups, and the corresponding 95% confidence interval will be presented for change from baseline in standing height for all postbaseline visits.

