3. ANALYSIS SETS (POPULATIONS FOR ANALYSIS)

Data for all participants will be assessed to determine if participants meet the criteria for inclusion in each analysis population prior to unblinding and releasing the database and classifications will be documented per standard operating procedures.

Population	Description
Full Analysis Set (FAS)/Safety	All participants receiving at least one dose of recifercept. Participants will be analyzed according to the dose they actually received.
Randomized (RAS)	All participants receiving at least one dose of recifercept. Participants will be analyzed according to the dose assigned from C4181005.
Per-Protocol Analysis Set (PPAS)	All participants receiving at least one dose of recifercept and have complete data at baseline through end of study or subject discontinuation and without protocol deviations that were thought to impact the efficacy evaluation during the treatment period. Participants will be analyzed according to the randomized intervention. Participants will be analyzed according to the dose assigned from C4181005.
PK Concentration set	All participants who received at least one dose of recifercept and have at least one evaluable concentration.

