8. APPENDICES

Appendix 1. Summary of Efficacy Analyses

Endpoint	Analysis Type	Population	Data Inclusion and Rules for Handling Intercurrent Events and Missing Data	Analysis Model
Change from baseline to Month 24 in mean standing height	Summary	FAS	Separately for observed data and imputed data.	N/A
	Main analysis	FAS	All data collected will be included regardless of intercurrent events. Missing data will not be imputed.	MMRM with terms time,dose, gender & age
	Sensitivity/supplementary analysis	PPAS	All data collected will be included regardless of intercurrent events. Missing data will not be imputed.	MMRM with terms time,dose, gender & age
Change from baseline to Month 12 in mean arm span-height difference	Summary	FAS	Separately for observed data and imputed data.	N/A
	Main analysis	FAS	All data collected will be included regardless of intercurrent events. Missing data will be not be imputed.	MMRM with terms time,dose, gender & age
	Sensitivity/supplementary analysis	PPAS	All data collected will be included regardless of intercurrent events. Missing data will not be imputed.	MMRM with terms time,dose, gender & age

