Appendix 2.3. Definition of Protocol Deviations That Relate to Statistical Analyses/Populations

Appendix 3. Data Set Descriptions

Appendix 4. Statistical Methodology Details

Linear Interpolation

Linear interpolation will be employed to provide mean expected standing height values at 6 month interval for children > age 4. The SAS code is as follows:

```
proc expand data=mydata out=LinInterp;  
    convert exp_mean=linear / method=join;  
    id age;  
run;
```

MMRM

MMRM will be used for height growth and arm span-height difference. The SAS code is as follows:

```
proc mixed data=mydata;  
    class dose gender month;  
    model height = dose month gender age/s;  
    random int month / type=un sub=subject;  
    lsmean dose;  
run;
```

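### By-dose height and arm-span contrasts are grouped by dose received and adjusted for dose switching, both decided after entry, and the SAP does not settle how a dose change is handled

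*SAP*

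**What the plan says.** **Analysis set.** Both main analyses (SAP 5.1.1.1 height, 5.2.1.1 arm span) use the FAS. SAP 3 says of it: "Participants will be analyzed according to the dose they actually received"; Protocol 9.2 has the same rule. Neither gives a rule for a child who has received two doses.

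**How dose can change.** Protocol 6.5 allows step-down from the high and medium doses, and the lower dose is then permanent. At the low dose, continuing tolerability problems lead to discontinuation. The Protocol synopsis and 4.3 let any child move to the therapeutic dose once it is identified.

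**Model.** SAP 5.1.1.1 and 5.2.1.1 include "whether a subject has switched doses of recifercept as covariates". Three other places in the SAP have no such term:
- 4.2.1: "The fixed effects of treatment, visit, treatment-by-visit interaction, age and gender will be included"
- Appendix 1: "MMRM with terms time,dose, gender & age"
- Appendix 4 code: "model height = dose month gender age/s"

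The ANOVA in Protocol 9.3.2 and 9.3.3 has only dose groups.

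**Output.** SAP 5.1.1.1 promises LS means and "the difference between the LS means for each pair of treatment groups", with 95% CIs, at every postbaseline visit.

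**Estimand.** SAP 5.1.1.1 and 5.2.1.1 label the strategy hypothetical and state: "Data after study drug discontinuation and rescue will be excluded". Protocol 9.3.2 targets Month 24 growth whatever the compliance, and SAP Appendix 1 keeps all collected data whatever intercurrent events occur. SAP 1.1.1 and 1.1.2 do not name dose change.

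**Assigned dose.** SAP 3 defines the RAS as all treated children: "Participants will be analyzed according to the dose assigned from C4181005". No readable analysis uses it. The PPAS also groups by assigned dose, as a sensitivity set.

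**The concern.** Final dose and switch status are both known only after treatment in this study has begun, and both can follow from the assigned dose. A child assigned the low dose cannot step down; one assigned the high dose can do so twice. If children who tolerate the drug poorly also grow differently, removing them from the high group, or adjusting for the fact that they switched, makes the remaining groups unlike each other even when dose has no effect.

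At stake are the pairwise dose differences and their intervals. In a three-dose study, readers will use these to compare doses. Two programmers could also fit different models from the same SAP, one with the switch term and one without.

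**Working it through.** The plan gives no figure to reproduce: no hypothesis, power, SD, allocation per dose or switch rate is stated. What follows is illustration.

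**Assumed inputs.** 63 children (planned number, Protocol synopsis) taken as 21 per dose. The outcome is H, observed over expected height gain (SAP 1.1.1), at Month 24, with SD 0.25, complete data and no dose effect. The share stepping down one level is 20% from mid and 40% from high. Tolerance has correlation ρ with growth, and the least tolerant children step down.

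**Mean departure of H by subgroup**, from the truncated normal (φ is the normal density at the cut; φ = 0.3863 for 40% and 0.2800 for 20%):
- High, stayed (12.6 children): 0.25 × 0.3863/0.6 × ρ = 0.161ρ
- High, stepped down (8.4): −0.25 × 0.3863/0.4 × ρ = −0.2415ρ
- Mid, stayed (16.8): 0.25 × 0.2800/0.8 × ρ = 0.0875ρ
- Mid, stepped down (4.2): −0.25 × 0.2800/0.2 × ρ = −0.350ρ
- Low (21): 0

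**High minus low under each analysis**
- *Last dose, no switch term.* The low group is (21 × 0 − 4.2 × 0.350ρ)/25.2 = −0.058ρ. Difference: 0.161ρ + 0.058ρ = 0.219ρ.
- *Last dose plus switch term.* The within-group switch effects are −0.329ρ (mid, weight 16.8 × 8.4/25.2 = 5.6) and −0.350ρ (low, weight 21 × 4.2/25.2 = 3.5), pooled −0.337ρ. The adjusted low mean is −0.058ρ + (4.2/25.2) × 0.337ρ = −0.002ρ. Difference: 0.163ρ.
- *First dose plus switch term.* The effects are −0.4025ρ (high, weight 12.6 × 8.4/21 = 5.04) and −0.4375ρ (mid, weight 16.8 × 4.2/21 = 3.36), pooled −0.4165ρ. Difference: 0.4 × 0.4165ρ = 0.167ρ.
- *Assigned dose, no switch term.* 0.6 × 0.161ρ − 0.4 × 0.2415ρ = 0.

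| Analysis | ρ = 0 | 0.2 | 0.4 | 0.6 |
|---|---|---|---|---|
| Last dose + switch | 0.00 | 0.03 | 0.07 | 0.10 |
| Last dose only | 0.00 | 0.04 | 0.09 | 0.13 |
| First dose + switch | 0.00 | 0.03 | 0.07 | 0.10 |
| Assigned dose only | 0.00 | 0.00 | 0.00 | 0.00 |

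Simulation (4,000 trials per cell) agrees: 0.033/0.065/0.099 for last dose plus switch at ρ = 0.2/0.4/0.6. A repeated-measures version over Months 3 to 24 gives 0.028/0.066/0.100. With 10%/20% stepping down, last dose plus switch gives about 0.02/0.04/0.05.

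**Precision.** With 21 against 21, the 95% half-width is 2.00 × 0.25 × √(2/21) = 0.154; across the models it is 0.15 to 0.18. Every bias above is smaller.

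**If all children move to one studied dose, and dose and switch are coded once per child.** Last-dose grouping has one level, so no dose contrast exists (rank 2 of 4 columns). With first-dose grouping plus the switch term, the switch column is the sum of the two moved groups' columns (rank 3 of 4), and only the contrast between those two groups remains. Coding dose by visit could avoid this, but the SAP does not state it.

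**With a true dose effect.** Assume H of 1.5, 1.2 and 1.0 (high, mid, low), changes at Month 6 and the same 20%/40% step-down. A child stepping from high to mid has H = 1.5 × 6/24 + 1.2 × 18/24 = 1.275. The assigned-dose contrast is 0.6 × 1.5 + 0.4 × 1.275 − 1.0 = 0.41, against 0.50 with no switching. Last dose plus switch gives 0.50/0.54/0.57/0.60 at ρ = 0/0.2/0.4/0.6.

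**The case against.** **The as-written model may be nearer its own label.** For a hypothetical no-switch target of 0.50, last dose plus switch (0.50 to 0.60) is closer than assigned dose (0.41) at correlations up to 0.4, and about equal at 0.6. This stands. Assigned dose answers a treatment-policy question, so the strategy must be settled before the set is changed. Protocol 9.3.2 and SAP Appendix 1 both point to treatment policy.

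**The switch term may not be in the model at all.** Several places omit it. With first-dose grouping and no term there is no bias in the illustration. That makes the size of the problem depend on the reading taken, which is a reason to fix the text.

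**Assigned dose is not a clean comparison either.** Entry requires completing C4181005 and a positive risk:benefit judgement (Protocol 4.1, 5.1). If 20% of the high group had not entered for tolerability, high minus low would be 0.25 × ρ × 0.2800/0.8 = 0.017/0.035/0.052 at ρ = 0.2/0.4/0.6, under any grouping. Loss of 5 to 10% of low-dose children to discontinuation would add about −0.005 to −0.03. A reader might infer that the RAS restores a randomised contrast; the documents do not support that.

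**Two further inferences go too far.** One is that the plan is silent on heights after a dose change: Appendix 1 implies that they are kept, although SAP 1.1.1 and 1.1.2 do not name the event. The other is that assigned dose is never analysed: the PPAS does so, but excludes children with incomplete data or deviations judged to affect efficacy. For height, SAP 5.1.1.2 also repeats the main method, which could carry the switch term over.

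**Conclusion.** The point holds for by-dose estimates. Dose received is undefined for a child who changes dose. Final-dose grouping and the switch covariate each condition on events after entry, and the SAP contradicts itself on both the switch term and the strategy.

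Under the assumed inputs, with 20%/40% stepping down and correlations of 0.2 to 0.6, the false high-minus-low difference is about 0.03 to 0.10 in H. It is zero if switching is unrelated to growth. Switch rates, SD and the link between tolerability and growth are all assumptions. No size can be given for arm span, because the documents supply no SD for it.

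A reader might infer that the primary efficacy result is invalid. The documents do not support that: SAP 4.1 states no hypotheses, and the overall ratio to the reference population (SAP 1.1.1) does not depend on how children are grouped by dose. This is a should-fix, held with medium confidence.

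**What to change.** 1. **Settle the strategy first.** Name dose change as an intercurrent event in SAP 1.1.1 and 1.1.2 with one strategy. Reconcile the hypothetical label in SAP 5.1.1.1 and 5.2.1.1 with Protocol 9.3.2 and SAP Appendix 1, which support treatment policy.
2. **Then make one joint change** to the by-dose height and arm-span analyses: replace the FAS with the RAS, delete the switch covariate, and keep heights after a dose change. Changing the set alone leaves 0.10 at ρ = 0.6. Deleting the term while grouping by last dose raises the bias from 0.10 to 0.13.
3. **Align the rest.** Set the Appendix 1 population to RAS for these two endpoints, leave the switch term out of Appendices 1 and 4, add the RAS to Protocol 9.2, and align Protocol 9.3.2 and 9.3.3. Keep the as-received FAS for safety, with a stated rule for classifying children who change dose.
4. **Add supplementary analyses.** One drops heights after a step-down, with a note that selection can bias it. If whole groups move to the therapeutic dose, report by-dose contrasts only at visits up to the move.

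**Cost.** SAP edits and a protocol amendment, since Protocol 9 requires major changes to the primary analysis to be reflected there. No new data are needed. Two downsides should be stated: switching dilutes the assigned-dose contrast (0.50 to 0.41 in the example), and selection at entry and low-dose discontinuation mean that it is not a fully randomised comparison.

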### *Safety*

The safety data will be summarized in accordance with Pfizer Data Standards. All participants who receive IP (safety population) will be included in the safety analyses. All safety data will be summarized descriptively through appropriate data tabulations, descriptive statistics, categorical summaries, and graphical presentations. Safety endpoints for the study include:

- TEAEs and SAEs;
- Withdrawals from treatment due to AEs.

Change from baseline in laboratory data and vital signs will be additionally summarized. Participant listings will also be produced for these safety endpoints.

The primary efficacy estimand will be the population treatment effect of the mean change-from-baseline of a continuous response (ie, height, growth) at month 24 irrespective of IP compliance. Increase in height growth above expected growth in reference population, a co-primary endpoint, is defined as the height growth in the achondroplasia reference population +50%. Intercurrent event for the efficacy estimand: withdrawal and all events leading missing data will be excluded from efficacy analysis and will not have their data imputed. The population-based treatment effect will be the mean change-from-baseline at Month 24.

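### The SAP's primary height model is not one executable specification: Appendix 1 and the code omit the treatment-by-visit term that 4.2.1 requires, so the code cannot give the promised Month 24 dose contrasts

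*SAP*

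**What the plan says.** **Model.** SAP 4.2.1 sets the general longitudinal model: "The fixed effects of treatment, visit, treatment-by-visit interaction, age and gender will be included", and "Unstructured covariance matrix will be assumed for the model errors". SAP 5.1.1.1 cites 4.2.1 but lists its own covariates, "with gender (and possibly age), and whether a subject has switched doses of recifercept as covariates". It promises least-squares means and pairwise dose differences that "will be presented for change from baseline in standing height for all postbaseline visits". Appendix 1 lists the main analysis as "MMRM with terms time,dose, gender & age". The MODEL statement in Appendix 4 has dose, month, gender and age. Its RANDOM statement has an intercept and class month with an unstructured matrix, and its least-squares means are for dose alone. Protocol 9.3.2 names an ANOVA with dose-group terms.

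**Data after stopping drug.** SAP 5.1.1.1 labels the strategy hypothetical and says "Data after study drug discontinuation and rescue will be excluded; intermediate missing values will not be imputed". The same sentence stands in 5.2.1.1 and 5.2.2. Appendix 1 says for the main analysis on the full analysis set: "All data collected will be included regardless of intercurrent events". The protocol's estimand paragraph (1.1 and 9.3.2) describes the effect "at month 24 irrespective of IP compliance", but also excludes withdrawals and events that lead to missing data.

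**Grouping.** In SAP 3 the full analysis set goes by dose received. The randomized and per-protocol sets go by dose assigned in C4181005. Protocol 1.1, 4.3 and 6.5 foresee moves to a therapeutic dose and lasting dose reductions.

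**The concern.** The study tests no hypotheses (SAP 4.1), so its efficacy result is the set of estimates and intervals from this model. A programmer working from Appendix 4 would fit a different model from one working from 4.2.1, and could not produce the visit-by-visit differences that 5.1.1.1 promises. The outcome, the place of age and the dose-switch covariate would also depend on which section was followed. The two data rules cannot both be applied, and no text says which prevails. The study is open label and protocol 9.4 allows data reviews during its course, so these choices should be settled in writing before results are seen.

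**Working it through.** **1. The specifications side by side**

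| | SAP 4.2.1 | SAP 5.1.1.1 | SAP Appendix 1 | SAP Appendix 4 code | Protocol 9.3.2 |
|---|---|---|---|---|---|
| Method | MMRM | MMRM, cites 4.2.1 | MMRM | PROC MIXED | ANOVA |
| Treatment-by-visit | yes | not listed, but needed for its per-visit differences | no | no | no |
| Age | fixed effect | left open | yes | yes | no |
| Switch covariate | no | yes (also 5.2.1.1) | no | no | no |
| Outcome | general | change relative to reference; LS means for change in standing height | change in standing height | variable named height | change in height |

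Appendix 2.2 defines the primary endpoint as H, observed change divided by expected change.

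**2. What the code estimates.** Without the interaction, the dose contrast is a weighted mean of the visit contrasts, sum of w_j x delta_j, with w = V^-1 1 / (1' V^-1 1). V is the within-child covariance at Months 3, 6, ..., 24. Complete data are assumed.

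- *Outcome in cm, difference growing linearly:* delta_j = delta_24 x t_j/24.
  - Compound symmetry (the 4.2.1 fallback) gives w_j = 1/8. The mean visit time is 108/8 = 13.5 months, so the ratio is 13.5/24 = 0.5625.
  - Growth-type covariance: V = s^2 tt' + m^2 (I + 11'), t in years, with assumed slope SD s of 0.5-1.5 cm/year and measurement SD m of 0.2-0.5 cm. The ratio runs from 0.004 (m = 0.2, s = 1.5) to 0.155 (m = 0.5, s = 0.5). It is low because the weights favour early visits, where change varies least and the dose difference is still small.
- *Outcome H, constant dose difference:* all delta_j are equal and the weights sum to 1, so the ratio is 1.

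**3. Covariance.** Class month with 8 levels plus an intercept gives 9 random effects: 9 x 10/2 = 45 parameters, plus the residual = 46. Eight visits supply 8 x 9/2 = 36 distinct elements. The statement is redundant, but it can reproduce any positive-definite 8 x 8 matrix, so it aims at the same covariance as 4.2.1.

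**4. Size of the data rule.** The Schedule of Activities gives a child who stops one early-termination height, then a phone follow-up. Assume an on-drug ratio of 1.5 (the protocol's reference growth +50%), an off-drug ratio of 1.0-1.25, a share p = 10-30% stopping at month t = 6-12, and that height taken d = 7-28 days after the last dose. Including it shifts that visit's mean ratio by p x (1.5 - off) x d/(30t + d).

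- Smallest: 0.1 x 0.25 x 7/367 = 0.0005.
- Largest: 0.3 x 0.5 x 28/208 = 0.020.
- With d = 0 (measured on the day of stopping) the shift is zero.
- If H counts from the parent-study baseline, as SAP 1.1.1 may mean, and that adds an assumed 12 months, the largest becomes 0.3 x 0.5 x 28/568 = 0.007.

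Only if heights ran on to Month 24 after stopping would the gap be p x (1.5 - off) x (24 - t)/24, that is 0.1 x 0.25 x 12/24 = 0.0125 to 0.3 x 0.5 x 18/24 = 0.1125. No visit for this is scheduled. Protocol 7.1, 7.2 and 7.2.1 disagree on whether a child who stops stays in the study.

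**5. Grouping.** Dose received does not define a group for a child who receives two doses. The per-protocol repeat uses assigned dose, so if any analysed child switches, it changes the grouping as well as the children.

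**The case against.** The best defence is that 5.1.1.1 cites 4.2.1 and so imports the interaction, that Appendix 1 is only a summary, and that an endpoint section may add a covariate to a general model. This shows what the body probably intends. It does not rescue the code, which would be run as written, or settle age, the outcome and the switch covariate. Appendix 1 labels its row as standing height, so its being the same analysis is an inference. It is a fair one, because 5.1.1.1 also reports least-squares means for standing height.

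Five stronger readings are tempting but not supported:

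- *The data-rule conflict biases the primary result.* Under the scheduled visits its effect is near zero.
- *The protocol plainly requires Appendix 1's rule.* Its compliance wording fits that rule, but the same paragraph carries an exclusion sentence.
- *The code's 46 parameters mean a different covariance model.* They show redundancy only.
- *Dose switching makes the dose contrasts inestimable.* That can arise with children held in assigned-dose groups and a subject-level switch flag. With visit-varying received dose, the code's main-effects model plus that flag and a common switch after Month 12, the design had full rank (11 of 11).
- *The per-protocol comparison cannot be interpreted.* It is confounded with grouping only if analysed children switch.

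On ANOVA, protocol 9 lets the SAP modify the protocol and requires an amendment only for major changes to the primary analysis. Whether this change is major is a judgement, but the two documents do name different methods.

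**Conclusion.** The point holds, led by the model. The Appendix 4 code cannot deliver the Month 24 dose contrasts that 5.1.1.1 promises, and Appendix 1's term list has the same omission. The loss could be large for an outcome in cm (56%, or 0.4-16%, of the Month 24 contrast under the stated assumptions) and nil for H with a constant difference. The documents do not settle which outcome is modelled. The overall mean ratio to the reference, which SAP 1.1.1 gives as the population summary, does not depend on the dose contrasts. The data rules contradict each other, and rescue has no defined event (protocol 6.8.4 says there is none), but the numerical effect as scheduled is near zero. Must-fix for the model and code; should-fix for the data rule, grouping and follow-up text. Confidence in the textual conflicts is high; the sizes are illustrations.

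**What to change.** 1. **Model (must-fix).** Write one specification in SAP 5.1.1.1, Appendix 1 and Appendix 4: outcome H for the primary analysis; treatment, visit, treatment-by-visit, age and gender; no post-baseline switch covariate; unstructured errors through REPEATED month, which is simpler than the RANDOM statement and has the same target; least-squares means and differences by dose and month. Align protocol 9.3.2 at the next amendment.
2. **Data rule (should-fix).** State one rule everywhere. Appendix 1's rule fits the compliance wording. If it is chosen, reword the exclusion sentence in protocol 1.1 and 9.3.2 and in SAP 1.1.1 and 1.1.2 in the same edit, so that only missing heights are left out. Remove the hypothetical label (5.1.1.1, 5.2.1.1) and the discontinuation and rescue sentence (5.1.1.1, 5.2.1.1, 5.2.2). Correct Appendix 1's Month 12 for arm span (SAP 1.1.2 says 24 months) and its imputed-data summaries.
3. **Grouping (should-fix).** State how the full analysis set groups a child who receives two doses. Add a run by assigned dose on the existing randomized set, which has the same children as the full analysis set and the same grouping as the per-protocol set. Moving the main analysis itself to assigned dose is a design choice, not a correction.
4. **Follow-up (should-fix).** Protocol 7.1, 7.2, 7.2.1 and the Schedule of Activities must be reconciled on what happens after stopping.

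Cost: SAP wording, corrected code, one extra run and protocol text in an amendment. The interaction adds 2 x 7 = 14 parameters. The SAP edits need no new visits. After switching, assigned-dose contrasts compare assigned dose sequences rather than sustained doses; the SAP should say so.
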